2. STUDY OBJECTIVES

This study aims to achieve a greater understanding of how different ways of presenting AMR to the public can influence their attitudes towards AMR, their comprehension and recall of the topic, and whether this can affect their intended future behaviour.

Primary objective:

Identify the best way of framing "Antimicrobial Resistance" to the public, in a way that resonates maximally and consequently shifts their attitudes towards AMR and its implications.

Secondary objectives:

- Identify which method of framing AMR is most likely to improve comprehension of antimicrobial resistance

Exploratory objectives

[figure not shown]
- Explore which method of framing AMR has the best recall from participants
- Identify which method of framing AMR most influences intent particularly with respect to future antibiotic use
- Explore the differing impact of different ways to present AMR on population subcharacteristics, including age, ethnicity and previous antibiotic use.

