- **4. Randomisation.** The 4,000 participants will be randomised in a 1:1:1:1 ratio to one of four trial arms. This will be done within the platform at the individual level and will be computer generated. Participants will be blinded to the study arm that they have been assigned to.
- 5. Intervention. As demonstrated in Figures 2 and 3 below, participants will be shown one of four images. Each image will be of a poster at a bus stop and will contain information about antimicrobial resistance. Each of the four posters will have a different name for AMR displayed on them. The participant will be free to look at the image for as long as they wish to.
- 6. Survey Questions. Once participants have looked at the image, they will click through a series of survey questions. The full survey can be viewed in Appendix 1. The survey questions have been designed to evaluate the following:
 - **a. Recall.** Participants will be asked questions to see if they can remember the name for AMR they were presented with, what the poster was about, and what the term means
 - **b. Comprehension.** Participants will be asked questions to evaluate their understanding of AMR and what the solution might be
 - **c. Intent.** Participants will be asked to predict their likely behaviours if they had symptoms of a viral infection (visit their doctor, pharmacist, or ask for antibiotics). They will be asked their opinion on what a friend or relative might do in the same situation. Finally they will be asked about finishing the course of antibiotics.
 - d. Attitudes towards AMR (Sentiment). Participants will be asked to state their agreement on several statements relating to AMR.
 - e. Understanding of AMR and existing terms. Participants' familiarity with the various terms for AMR being tested, and their understanding of AMR

The survey incorporates some free text responses to further understand participants understanding of AMR, and what this term means to them. It is possible that some anonymised quotes may be published in any resulting study publications. This is made clear in the summary PIS and on the introduction slide that the participant will see before engaging with the survey.

7. **Demographics.** Participants will be asked to provide non-identifying demographic data, including their previous antibiotic use and whether they work in the healthcare sector.

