Recruitment will be open for specified covariates until the representative quotas are recruited, demonstrated in Table 1. Once the survey is advertised, survey completion and ongoing participant recruitment will continue in parallel. The recruitment window for the study will remain open until all participant groups are recruited at the defined size. If one participant sub-group is more difficult to recruit, the financial incentive for this sub-group will be raised as part of the pre-defined dynamic process.

Recruitment rates will determine the length of the recruitment and study period, however from previous experience we anticipate the total duration of the study to be 3 weeks.

The target for recruitment has been set at 4,000 participants based on power calculations for the primary outcome. Accepting a two-sided p-value of <0.05 as statistically significant, the study has been designed with 80% power to detect a minimal detectable effect size 6% between trial arms. This is based upon a likely outcome baseline of 60% for sentiment (attitudes to AMR) as referenced in previous similar studies by Wellcome (13), and a likely difference between trial arms as seen in other online trials (15).

Table 1: Participant recruitment targets to ensure representation of the U.K. population

Covariate Proportion to be recruited

Gender	
Women	50%
Men	50%
Age	
18-24	12%
25-54	53%
55+	35%
Region	
South & East	32%
North	23%
Midlands	16%
Scot/NI/Wales	16% (each country
	represented
	proportionately)
London	13%
Ethnicity	
White	82%
Asian (or Asian British)	9%
Black (or Black British)	4%
Mixed / Other	5%

Consent to participate.

Participants will receive the link for study via their own market research panel, who will hold any personally identifying data. This will not be available to the research team at BIT or ICL. The research team will only access anonymous data provided within the survey itself and anonymised demographic data provided by the market research panel.

Accessing the link to the online experiment and continuing with the online survey will be taken as implied participant consent for this study. Participants will be informed that they are free to leave the survey at any point during the process, and given instructions as to how to do so.

Study Duration

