The study will be launched on the 20th March 2024 and will stay open until participant recruitment has been fulfilled. Based on previous experience we anticipate the study duration to be 3 weeks. The participant will be involved in the study for approximately 5 minutes (the anticipated time taken to view the image and answer related questions), after which no further involvement will be required.

Data Analysis

Statistical analysis of anonymous survey data will be conducted by the named study team members at BIT, obtained directly from their Predictiv platform. This will be conducted at the individual participant level. The detailed analysis plan can be found in Appendix 1, and will cover the following key components:

1. Primary Outcome – Attitudes towards AMR (Sentiment). This will be conducted using a quasibinominal regression model

- 2. Secondary Outcome Comprehension of AMR. This will be conducted using a quasibinominal regression model
- 3. Exploratory Outcomes Each exploratory outcome will be analysed using a separate logistic regression for each outcome.

Regression will be adjusted for the following covariates: age, gender, income, region, ethnicity, education, employment status, prescribe antibiotics in job, first language, taken antibiotics in last year For the primary and secondary outcomes, the Benjamini-Hochberg procedure will be used to adjust for 3 comparisons (all treatment arms to control) within each outcome. There will be no multiple comparison correction for the exploratory outcomes.

Aggregate anonymised data will be transferred to researchers at ICL via secure email for further analysis and write up of the findings. These data will be stored securely in a password protected folder within Imperial College London's Sharepoint.

Data Storage

Aggregate anonymised data will be stored securely on ICL servers, only accessible by the ICL research team. This will be stored for 10 years in line with ICL policy on data storage.

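### Past-year antibiotic use is self-reported after the arm-specific poster but used as a regression covariate, so the adjusted arm contrast is open to a small, avoidable bias

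*Combined protocol and SAP*

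**What the plan says.** Section 3, Study Design, sets out a numbered participant flow: randomisation (4), poster (5), survey questions on recall, comprehension, intent and sentiment (6), then demographics (7). On the poster it says "Each of the four posters will have a different name for AMR displayed on them". On step 7 it says "Participants will be asked to provide non-identifying demographic data, including their previous antibiotic use and whether they work in the healthcare sector".

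The Data Analysis text of the same section adjusts the regressions for ten covariates, the last three being "prescribe antibiotics in job, first language, taken antibiotics in last year". The supplied text gives no model without the antibiotic-use item.

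Section 2 lists an exploratory objective on whether the effect of framing differs across population characteristics, "including age, ethnicity and previous antibiotic use". Under Consent to participate, section 3 mentions "anonymised demographic data provided by the market research panel". It does not list those items, and step 7 has the participant supply antibiotic history.

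**The concern.** A covariate helps a randomised comparison when treatment cannot affect its recorded value. Actual use in the past year meets that condition, but the answer given after the poster may not. A name that makes AMR more salient could change willingness to admit recent use, or recognition that a past medicine was an antibiotic. The trial's own hypothesis is that framing changes understanding, attitudes and intended antibiotic behaviour, so some effect on this answer is plausible. That is inference; the documents offer no evidence of it.

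Only a shift that differs between arms matters. All four posters concern AMR, so an effect of the shared topic, or of the questions asked in between, is largely common and cancels. A differential shift would move the adjusted contrast by roughly the shift times the within-arm association between reported use and outcome, in either direction. Subgroups defined by reported use are more exposed, because misreporting changes who is in them.

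The point is confined to this item. No comparable mechanism is claimed for prescribing in one's job or for general demographics.

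**Working it through.** **Inputs from section 3.** 4,000 participants allocated 1:1:1:1, so 1,000 per arm; 60% baseline; two-sided 0.05; "80% power to detect a minimal detectable effect size 6% between trial arms", read as 60% v 66%.

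**The plan's own figure.** With pooled variance, n = [1.96·√(2·0.63·0.37) + 0.842·√(0.24 + 0.2244)]² / 0.06² ≈ 1,016 per arm, or 4,064 in total. Power at 1,000 per arm is 79.4%. The stated size reproduces closely, and this point does not change it.

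**Assumptions (not in the documents).** True use q = 35%; users score d = 5, 15 or 25 points lower; no true arm effect; truthful reporting in control; reported use in one arm shifted by s = 1, 3 or 5 points.

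**Bias of the adjusted contrast.** With no true effect the raw difference is zero, so the adjusted effect is −β × (difference in reported use), where β is the pooled within-arm slope of outcome on reported use. For under-reporting, put c = q − s. Then

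β = −d(1 − q)(q + c) / [q(1 − q) + c(1 − c)], and the adjusted effect is β·s.

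Example, d = 15 and s = 5: c = 0.30; β = −0.15 × (0.65 × 0.65) / (0.2275 + 0.21) = −0.1449; effect = −0.1449 × 0.05 = −0.72 points.

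The SE of an arm difference is √(2·0.6·0.4/1000) = 2.19 points, treating the outcome as binary. The per-comparison rejection rate is Φ(−1.96 + |b|/SE) + Φ(−1.96 − |b|/SE), where b is the bias.

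| User gap / shift (points) | Bias, under-reporting | Bias, over-reporting | Rejection rate (under-reporting) |
|---|---|---|---|
| 5 / 3 | −0.147 | +0.144 | 5.05% |
| 15 / 1 | −0.149 | +0.148 | about 5.05% |
| 15 / 3 | −0.440 | +0.432 | 5.46% |
| 15 / 5 | −0.724 | +0.702 | 6.26% |
| 25 / 5 | −1.207 | +1.170 | 8.54% |

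The contrast without the covariate is 0.000 in every row. Linear and logistic-link results agree to within 0.001 points. Varying true use over 25–45% moves the largest under-reporting case only from 1.20 to 1.21.

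**A wider grid.** With 30–40% users, gaps of 5 to 20 points and 5–30% of users under-reporting in one arm, the bias runs from 0.07 to 2.22 points, mostly under 1. If only favourable responders under-report, it runs from 0.01 to 1.47 points, and is non-zero even when true use is unrelated to the outcome.

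**Subgroups defined by reported use (q = 35%).**
- Under-reporting, reported non-users: bias = d·s/(1 − c). From 5 × 0.03/0.68 = 0.22 to 25 × 0.05/0.70 = 1.79 points.
- Over-reporting, reported users: bias = d·s/(q + s). From 5 × 0.03/0.38 = 0.39 to 25 × 0.05/0.40 = 3.13 points.
- SE at 350 per arm: √(2·0.24/350) = 3.7 points.

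**Precision lost by dropping the item.** R² = d²·q(1 − q)/0.24 = 0.0024, 0.0213 and 0.0592 for gaps of 5, 15 and 25. The SE ratio 1/√(1 − R²) is 1.001, 1.011 and 1.031. At a 15-point gap the SE goes from 2.17 to 2.19.

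**Would a by-arm test detect the problem?** At 1,000 per arm, power is 0.295 for 35% v 32% and 0.667 for 35% v 30%.

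**The case against.** The bias needs two things for which the documents offer no evidence: the displayed name must alter reporting by a different amount from the control name, and reported use must be related to sentiment. The larger cases are demanding. At 35% users, a 3-point shift means 3/35 = 8.6% of true users misreport because of the name, and a 5-point shift means 5/35 = 14%. Even 1.2 points is 20% of the 6-point target and 0.55 of an SE. The rejection rates treat the outcome as one binary item, although sentiment covers several statements in a quasibinomial model, and they ignore the Benjamini-Hochberg step. The subgroup analysis is exploratory, and its worst case is below one SE. Appendix 1, which holds the full survey and detailed analysis plan, was not among the documents reviewed and may already contain a model without the item. Tabulating reported use has its own limit: the 95% interval for a between-arm difference is about ±4.1 points, too wide to exclude a 3-point shift.

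Most of this stands. The rates are illustrations and do not estimate this trial's error rate. Omitting the covariate removes only this source of bias; section 4.4 deletes the data of people who withdraw, which can happen after randomisation, and that is a separate matter. None of it gives a reason to keep the item in the primary model: the precision gain is slight, and the randomised contrast does not need it.

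**Conclusion.** The concern holds as a low-cost improvement. It does not threaten the main conclusion. The order of steps and the covariate list are explicit, and no passage assigns antibiotic history to the panel data. If the name shown changes reporting differently across arms, the adjusted primary contrast is biased by about 0.15 to 1.2 points in the main cases, with either sign possible; if reporting is the same in all arms, this bias is zero. Subgroups defined by reported use could be off by 0.2 to 3.1 points. Apart from the 60% baseline and 1,000 per arm, every input is an assumption. Confidence is medium, because differential reporting is plausible but not shown and Appendix 1 could not be checked.

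**What to change.** Remove antibiotic use in the past year from the covariate sets of the primary and secondary models, and report the models that include it as sensitivity analyses. Tabulate reported use by arm with confidence intervals before interpreting any subgroup defined by it. Read the table descriptively: a significance test should not be a gate, and a null difference does not rule out a shift of the size considered. Prescribing in job can stay where it is. If Appendix 1 already has a model without the item, the change is only to make that model primary.

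The cost is one covariate of ten deleted, one table and one sensitivity model added, and an SE increase of about 0.1% to 3.1% under the assumed gaps. The survey, sample size and randomisation are unchanged. An optional alternative is to ask the item before randomisation. Its debatable downside is possible priming, which would be common to all arms.

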1.2 Study Rationale

It has been established that behavioural science can be applied to the problem of antimicrobial resistance, and therefore that behaviours that contribute to its aetiology can be addressed. However, it is not clear that the current phrasing and terminology used to describe this looming crisis – "Antimicrobial Resistance" is reaching or resonating with the public. This has been described in the literature but not explored adequately. Studies to date have engaged with experts and world leaders on how best to present the crisis to the public – but there has been limited public engagement and co-production when it comes to determining what the best way of doing so might be. This study aims to test new ways of naming / framing AMR that have been co-designed with the public.

As such, this study has been conceived in order to help answer the following research question: "Can we co-design a new way of framing the AMR crisis with the public, that is memorable, conveys meaning and inspires behaviour change?"

We hypothesise that a co-designed behaviourally informed way of framing AMR will resonate better with the public, improving understanding of AMR, attitudes towards AMR and will influence future AMR related behaviours (such as requesting antibiotics).

The null hypothesis for this study is that no alternative naming strategy is more impactful than Antimicrobial Resistance / AMR itself.

Intervention Design

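### The stated comparisons for sentiment and comprehension set each new name against control only, so they give no inference between names, although both objectives ask which framing is best

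*Combined protocol and SAP*

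**What the plan says.** The primary objective in section 2 begins "Identify the best way of framing". The secondary objective is "Identify which method of framing AMR is most likely to improve comprehension of antimicrobial resistance". Both ask for a choice among framings.

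Section 1.2 states a narrower null hypothesis: "no alternative naming strategy is more impactful than Antimicrobial Resistance / AMR itself".

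The Data Analysis text in section 3 gives each of the two outcomes a quasibinomial regression. It continues: "For the primary and secondary outcomes, the Benjamini-Hochberg procedure will be used" to "adjust for 3 comparisons (all treatment arms to control) within each outcome". Exploratory outcomes are handled separately ("There will be no multiple comparison correction for the exploratory outcomes") and are not part of this point.

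The sample-size text in section 3, under Participant Recruitment, claims "80% power to detect a minimal detectable effect size 6% between trial arms", from a "likely outcome baseline of 60% for sentiment". It does not say which pairs of arms are meant. The detailed analysis plan is referred to Appendix 1, which is not among the supplied documents; section 3 gives its key components.

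**The concern.** Four arms give six pairwise contrasts. The stated family holds the three that involve control and none of the three between new names. It therefore answers the section 1.2 null but offers no inference on the choice that section 2 sets as the aim.

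Two kinds of result leave the aim open. If several names beat control, the stated tests do not separate them. If one name is significant against control and another is not, that difference in verdicts is not evidence that the two names differ. In either case, a statement that one name is best would rest on no test or interval that the supplied text specifies.

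**Working it through.** **Inputs from the documents.** 4,000 participants allocated 1:1:1:1, so 1,000 per arm; two-sided 0.05; control at 60%; design effect 6%, read as percentage points (66%).

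**Assumptions.** All other true rates below. How sentiment items are scored is not visible, so the variance of a participant's score is taken as 100%, 70%, 50% or 30% of that of a single binary item. Covariate adjustment is ignored.

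**The plan's own figure.** For one comparison with unpooled variance:

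n per arm = [0.60×0.40 + 0.66×0.34] × (1.960 + 0.842)² / 0.06² = 0.4644 × 7.849 / 0.0036 = 1,012.5, so 1,013, or 4,052 in total.

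The pooled form gives 1,016 per arm, or 4,064 in total, 1.6% above 4,000. Power at 1,000 per arm is 79.4%. The stated size therefore reproduces for a single pairwise test at unadjusted 0.05.

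**What the stated family returns.** Simulation with 400,000 trials per scenario: two-sided z tests with unpooled variance, and Benjamini-Hochberg at 0.05 within the three control comparisons. Rates are listed control first. Results are percentages of trials.

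| True rates, and result | 100% of binary variance | 70% | 50% | 30% |
|---|---|---|---|---|
| 60/66/66/66: two or more names beat control | 78.8 | 92.3 | 98.4 | 99.97 |
| 60/66/66/66: all three beat control | 60.3 | 81.0 | 94.0 | 99.7 |
| 60/66/66/66: mixed verdicts among equal names | 28.0 | 15.5 | 5.4 | 0.3 |
| 60/66/66/69: two or more beat control | 87.4 | 96.1 | 99.3 | 99.99 |
| 60/63/63/66: two or more beat control | 32.7 | 45.6 | 59.5 | 80.8 |
| 60/60/60/66: two or more beat control | 3.1 | 3.1 | 3.1 | 3.1 |
| 60/60/60/66: exactly one beats control | 62.6 | 79.8 | 91.1 | 96.6 |

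In the last scenario the usual result is a single winner. It has been compared with control but not with the other two names.

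**What ranking would give.** Taking the highest observed name, with a binary item, picks the truly best one in about 87% of trials for 60/66/66/69% and 86% for 60/63/63/66%. When all three are equal, it still puts some name on top every time, each in about a third of trials.

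**Precision between names.** The 95% half-width for two new names at 66% is 1.96 × √(2 × 0.66 × 0.34 / 1,000) = 4.15 points for a binary item. Multiplying by √0.7, √0.5 and √0.3 gives 3.47, 2.94 and 2.27 points.

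**A strict rule.** Call a name best only if it beats AMR and both other new names, with the three between-name contrasts as their own Benjamini-Hochberg family. The first three rows give how often the truly best name meets the rule; the last two give how often some name is wrongly called best.

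| True rates | 100% | 70% | 50% | 30% |
|---|---|---|---|---|
| 60/66/66/69 (3-point lead) | 11.6 | 18.6 | 29.2 | 54.3 |
| 60/66/66/72 (6-point lead) | 66.6 | 85.2 | 95.9 | 99.9 |
| 60/60/60/66 (one name works) | 48.9 | 72.0 | 89.9 | 99.5 |
| 60/66/66/66 (all equal) | 0.8 | 0.8 | 0.8 | 0.8 |
| 60/60/66/66 (two equally good) | 3.9 | 4.4 | 4.8 | 5.0 |

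**The case against.** Selection does not require pairwise significance. The regression estimates every name against a common control, so adjusted estimates can be ranked, and the ranking is often right when a real leader exists. This stands. A reader might infer that the stated analysis cannot identify the best framing at all, and that goes too far. What is missing from the supplied text is a rule to rank by and a statement of the ranking's uncertainty.

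Section 3 summarises a detailed plan held in Appendix 1. This also stands. A reader might infer that the trial will name a winner with nothing pre-specified, but the documents do not support that, because the appendix was not available to check.

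The share of trials with two or more winners is not the rate of the fault. It depends on how many names work, the protocol does not plan for all three at 66%, and a lone winner is just as untested against its rivals. This stands, so those percentages illustrate the consequence and do not measure how often the problem arises.

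The three tests match the section 1.2 null, and rewording section 2 would close the gap. That is correct: the control tests are not in error. It does not remove the mismatch while section 2 reads as it does.

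**Conclusion.** The concern holds as a mismatch between objective and stated analysis, for sentiment and comprehension only. The family in section 3 addresses whether any new name beats AMR. It supplies no inference between new names, and the supplied text gives no selection rule in its place.

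If all three names reach the design effect, two or more beat control in about 79% to over 99.9% of trials, and truly equal names receive mixed verdicts in 28% to 0.3%. With graded rates of 60/63/63/66%, two or more beat control in about 33% to 81%. These figures assume 1,000 per arm, the stated 60% baseline, the assumed true rates for the names, and a score variance between 100% and 30% of a binary item. The conclusion is limited to what section 3 states, since Appendix 1 was not seen.

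**What to change.** Leave the three control comparisons as they are. For each of the two outcomes, add the three between-name contrasts from the same quasibinomial model, with confidence intervals, as a separate Benjamini-Hochberg family. Report the top-ranked name together with those not distinguishable from it, and call a name best only if it beats AMR and both other new names.

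Alternatively, reword both section 2 objectives to ask which framings outperform Antimicrobial Resistance / AMR, in line with section 1.2. If Appendix 1 already holds such contrasts or a selection rule, state them in the Data Analysis text of section 3.

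The cost is three contrasts per outcome or a change of wording. No further participants are needed, and the control tests and their power do not change. The drawback is power: a 3-point lead over rivals at 66% meets the strict rule in only about 12% to 54% of trials, so the trial may often have to report that no single best name was shown.
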